# 7.2.13 Clinical Safety Laboratory Evaluations

Samples of blood and urine (Table 2) are scheduled for collection as shown in Table 3 and Table 4. Repeat clinical safety laboratory evaluations may be conducted at the discretion of the Investigator.

Additional follow-up samples for clinical laboratory testing should be obtained as clinically indicated. A 3-mL serum aliquot will be collected at each time point and archived for safety testing as may be required by emergence of adverse conditions.

Participants with a white blood cell count  $\ge 15 \times 10^9$ /L, laboratory evidence of acute kidney injury, or an absolute neutrophil count of  $< 1 \times 10^9$ /L neutrophils at Screening are to be

excluded from the trial. Screening laboratory assessments may be repeated up to twice at the Investigator's discretion.

All clinical laboratory testing, with the exception of optional drug testing or on-site serum (at Screening only) or urine (during the Treatment Period) pregnancy testing for females of childbearing potential, will be performed by the central clinical laboratory.

Category	Analyte
Hematology	Complete blood count with differential.
Chemistry	
Coagulation	Activated partial thromboplastin time, prothrombin time, and international normalized ratio.
Urinalysis	
Screening only	
Pregnancy	Serum hCG for women of childbearing potential.

 Table 2:
 Clinical Laboratory Safety Tests

Abbreviations: hCG = human chorionic gonadotropin.

A laboratory test result that is judged by the Investigator as clinically significant will be recorded as an AE and will be monitored as described in Section 7.2.3.1.3. An event may include a laboratory or diagnostic test abnormality that results in the withdrawal of the participant from the trial, the temporary or permanent withdrawal of medical treatment, or further diagnostic work up. (NOTE: Abnormal laboratory or diagnostic test results at the Screening visit that preclude a participant from entering the trial or receiving IP are not considered AEs.)

# 7.3 Unscheduled Visit

# 7.3.1 Unscheduled Visit for New Diarrhea Episode

Participants are to report diarrhea promptly to the trial site at any time during the trial. For each new episode of diarrhea (> 3 unformed stools in 24 hours for 2 consecutive days) during the trial period, a stool sample for central laboratory testing must be collected. A central laboratory test is a requirement for this trial and should not be replaced with a local

laboratory test, unless under extenuating circumstances (e.g., central laboratory is closed due to pandemic). This sample should be collected before SOC CDI antibiotics are commenced.

If *C. difficile* testing is positive by central laboratory testing algorithm, an Unscheduled Visit should be arranged for the participant. If *C. difficile* testing is negative by the central laboratory testing algorithm, an Unscheduled Visit may be arranged at the discretion of the Investigator for the participant.

**NOTE:** Every effort will be made to conduct an on-site assessment/home visit at Unscheduled Visit. However, under extenuating participant circumstances that make an onsite visit/home visit not feasible and after all reasonable measures have been exhausted, a virtual/telephonic trial visit may be conducted.

- •
- •
- Perform physical examination (only if medically indicated).
- Inquire about concomitant medications and AEs since the last visit.
- Collect vital signs and weight (if medically indicated).
- Collect stool sample for shipment and processing at central laboratory. Samples will be used for molecular testing, including, but not limited to, 16S rRNA gene amplicon sequencing, \_\_\_\_\_\_, and safety testing.
- Perform laboratory testing, as clinically indicated, including testing stool for CDI using a *C. difficile* testing algorithm (Figure 8).
- •

# 7.3.2 Unscheduled Visit for Adverse Events

Procedures conducted at an Unscheduled Visit for indications other than a new episode of diarrhea are at the discretion of the Investigator. During unscheduled visits for AEs, medically appropriate samples previously obtained or to be collected, including but not limited to stool, urine, blood, bacterial isolate may be requested by the **Sponsor** for additional molecular characterization. Further details are described in the Laboratory Manual. NOTE: Under extenuating circumstances, an Unscheduled Visit may be conducted as a telephonic/virtual visit.

# 8 STATISTICAL METHODS AND DATA ANALYSIS

# 8.1 Trial Endpoints

Refer to Sections 2.1 and 3.3.

# 8.2 Overview of Statistical Analysis

This section outlines the statistical analysis strategy and procedures for the trial. If, after the trial has begun, but prior to any unblinding, changes are made to the primary endpoint definition, or the statistical methods related to the test of the primary hypothesis, then the protocol will be amended (consistent with *ICH Guideline E-9*). A stand-alone SAP will be

written to describe in detail all statistical analyses planned for the trial. It will be accompanied by mock tables, figures, and listings. The SAP will be finalized and approved by signatures and dates prior to database lock for Week 8. The SAP will take precedence over the protocol for details about the statistical analyses for the trial except as noted above. In addition to the SAP, other graphical representations of the results may be produced after review of the data (*post-hoc*).

Verbatim terms recorded for medical history conditions, surgical history procedures, and AEs will be mapped to a system organ class and preferred term using the MedDRA, and all prior and concomitant medications will be coded using the World Health Organization Drug Dictionary.

The IP blind will be maintained through Week 8. Participants, the Sponsor, Investigators, and all trial site personnel involved with the trial, carrying out trial procedures, evaluating participants, entering trial data, and/or evaluating trial data will remain blinded to treatment allocations until all participants have completed the Week 8 assessments and the database has been locked for the analysis at Week 8. The Investigators, trial site personnel, and participants will remain blinded until Week 24.

Planned interim analyses are described in Section 8.8. Participant-level unblinding will be restricted to the independent statistician who will be preparing the IA and who will have no other responsibilities associated with the trial.

# 8.3 Analysis Populations

Four analysis populations are planned for the trial:

[figure not shown]
Intent-to-treat population (ITT or All Randomized)	All participants randomized into the trial including those who were not exposed to any IP will be included in the ITT population. Participants in the ITT population will be analyzed according to the treatment group to which they were randomized. Th ITT population will be the primary analysis population for all efficacy analyses.		
The mITT population	All participants in the ITT population who receive at least 1 capsule of IP at Randomization (Day 1).		
Per-protocol population (PP population)	All participants in the mITT population who have received at least 80% of trial medication, completed 8 weeks of follow-up or had adjudicated CDI recurrence prior to the 8-week follow-up and did not have any major protocol deviation that affect the efficacy or safety of the IP.		
Safety population	All enrolled participants who received at least 1 capsule of IP. Unless otherwise stated, the Safety population will be the default analysis population for		

all safety analyses. Analyses of safety will be performed based on treatment received, even if different from the treatment group to which participants were randomized. All safety analyses will be performed on the Safety population.

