### 2.1 Primary Efficacy Objective, Endpoint, and Estimand

Primary Objective	Primary Endpoint
To evaluate the efficacy of a single oral dose of CP101 compared to placebo following SOC CDI antibiotics in preventing CDI recurrence in participants with recurrent CDI	Proportion of participants experiencing a CDI recurrence through Week 8 based on adjudication

The primary clinical question of interest is:

What is the difference in the proportions of participants experiencing CDI recurrence through 8 weeks after randomization to CP101 vs placebo in participants with recurrent CDI regardless of discontinuation of investigational intervention for any reason or change in background medication (dose and product)?

The estimand is described by the following attributes:

• Population:

Adult participants with recurrent CDI who have completed SOC CDI antibiotics for their qualifying episode

• Endpoint:

CDI recurrence through 8 weeks post randomization

• Treatment condition:

CP101 or placebo on Day 1 with 8 week follow-up for recurrence regardless of discontinuation of investigational intervention for any reason, or change in background medication (treatment policy strategy).

• Remaining intercurrent events:

The intercurrent events "intervention discontinuation for any reason" and "change in background medication (dose and product)" are addressed by the treatment condition of interest attribute.

The following intercurrent events will result in an outcome of "recurrence" for the primary efficacy analysis:

- Initiation of rescue medication for CDI (fecal microbiota transplantation [FMT] or full course of SOC antibiotics) prior to 8 weeks post randomization
- Occurrence of *C. difficile*-related diarrhea prior to 8 weeks in a participant who does not qualify for Part B of the study, per central lab testing algorithm, and discontinues the study for any reason
- Participants who enter into Part B of the study however, the *C. difficile*-related diarrhea episode is adjudicated as "no recurrence" by the AB
- Participants who die or experience another debilitating event prior to 8 weeks, which precludes continued participation in the study
- Participants who withdraw consent prior to 8 weeks after randomization
- Participants who are lost to follow-up prior to 8 weeks after randomization

There are no other intercurrent events anticipated at this time.

• Population-level summary:

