# 8.4 Efficacy Analysis

#### 8.4.1 Primary Endpoint

The primary efficacy endpoint is defined as the proportion of participants with CDI recurrence through Week 8 based on adjudication calculated as the number of participants with CDI recurrence through Week 8 divided by the total number of participants in the analysis population. Investigator evaluation of a new episode of diarrhea will be adjudicated by an independent AB to confirm CDI recurrence in a blinded fashion prior to database lock.

For the primary efficacy analysis, the active treatment group will be compared to the placebo group.

The primary efficacy endpoint analyses will be repeated using the mITT and PP populations defined in Section 8.3.

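### The per-protocol set drops early leavers whose C. difficile-related failure was not confirmed by adjudication, although Section 2.1 scores them as recurrences

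*Protocol*

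**What the plan says.** Section 8.3 builds the PP set from the mITT set. A participant needs at least 80% of trial medication, no major deviation affecting efficacy or safety, and must have "completed 8 weeks of follow-up or had adjudicated CDI recurrence prior to the 8-week follow-up". For someone who stops before Week 8, the only way in is an adjudicated recurrence.

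Section 2.1 defines the primary outcome more widely: "The following intercurrent events will result in an outcome of 'recurrence' for the primary efficacy analysis". Its list includes:

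- rescue treatment for CDI, by fecal transplant or a "full course of SOC antibiotics) prior to 8 weeks post randomization";
- C. difficile-related diarrhea before Week 8 "in a participant who does not qualify for Part B of the study, per central lab testing algorithm, and discontinues the study for any reason";
- entry into Part B although the "diarrhea episode is adjudicated as 'no recurrence' by the AB";
- death or another debilitating event that ends participation;
- withdrawal of consent, and loss to follow-up.

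Section 8.4.1 carries the endpoint into the smaller sets: "The primary efficacy endpoint analyses will be repeated using the mITT and PP populations defined in Section 8.3". Section 6.1 says that the visit schedule restarts for participants who enter Part B.

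**The concern.** A per-protocol set normally leaves people out for poor adherence or for a missing outcome. The C. difficile-related failures in Section 2.1 fit neither reason, because the protocol gives them an outcome, and that outcome is failure. Yet of two participants who both fail and both leave before Week 8, the one confirmed by the AB stays in the PP set and the other goes. Event-free completers who meet the remaining criteria all stay.

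That is selection on the outcome being analysed, after randomization. A gap between the PP and ITT results could then come from this clause and not from exclusions for dosing or protocol deviations, and a reader of the report could not tell the two apart.

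**Working it through.** **Text check, event by event, for a dosed participant**

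- *Rescue medication for CDI.* Scored as recurrence in Section 2.1. Dropped from PP only if the participant also leaves before Week 8 without an adjudicated recurrence. A rescue user who reaches Week 8 stays, subject to the deviation rule.
- *C. difficile-related diarrhea, not qualifying for Part B, then discontinuation.* Dropped if follow-up ends before Week 8, unless the AB confirms a recurrence.
- *Part B entry, AB rules no recurrence.* There is no adjudicated recurrence by definition. Dropped if the 8 weeks in Section 8.3 mean Part A follow-up. Section 8.3 does not say which follow-up counts.
- *Death or debilitating event.* Dropped unless an adjudicated recurrence came first. Whether to keep such cases in a PP set, above all those unrelated to CDI, is a matter of convention.
- *Withdrawal of consent, loss to follow-up.* Dropped. This is usual, since the true outcome is unknown.

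**Illustration of size**

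The protocol states no figure for this point, so there is none to reproduce. Inputs:

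- N = 324 (Section 8.10), allocated 2:1 (Section 3.1): 324 × 2/3 = 216 on CP101 and 324/3 = 108 on placebo.
- *a* = share with adjudicated recurrence. Assumed 22% vs 33%, or 25.5% vs 38.5%. The second pair is 100% minus the earlier trial's 74.5% and 61.5% (Sections 1.5.2 and 1.6). The protocol prints those as recurrence rates, but they fit its claim of a lower rate on CP101 only if read as non-recurrence.
- *f* = share of early leavers scored as recurrence without AB confirmation and dropped from PP. Assumed; the documents give none.
- No other PP exclusions are applied, so that the effect of this clause stands alone.

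Rate under Section 2.1 = a + f. PP rate = a/(1 − f). The fall within an arm is (a + f) − a/(1 − f) = f(1 − a − f)/(1 − f), which is positive whenever f > 0 and a + f < 1.

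Worked case, 3% vs 6% dropped:

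- Section 2.1 rates: 22 + 3 = 25% and 33 + 6 = 39%, difference 14.0 points.
- PP rates: 0.22/0.97 = 22.7% and 0.33/0.94 = 35.1%, difference 12.4 points.

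All cases, CP101 vs placebo:

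| a | f | participants dropped | Section 2.1 rates | PP rates | difference, points |
|---|---|---|---|---|---|
| 22% vs 33% | 2% vs 3% | 4.3 and 3.2 | 24.0% vs 36.0% | 22.4% vs 34.0% | 12.0 to 11.6 |
| 22% vs 33% | 3% vs 6% | 6.5 and 6.5 | 25.0% vs 39.0% | 22.7% vs 35.1% | 14.0 to 12.4 |
| 22% vs 33% | 5% vs 8.5% | 10.8 and 9.2 | 27.0% vs 41.5% | 23.2% vs 36.1% | 14.5 to 12.9 |
| 25.5% vs 38.5% | 5% vs 5% | 10.8 and 5.4 | 30.5% vs 43.5% | 26.8% vs 40.5% | 13.0 to 13.7 |

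The last row shows why the direction is open. With equal dropped shares, the arm with the lower adjudicated rate falls more: 0.05 × 0.695/0.95 = 3.7 points on CP101 against 0.05 × 0.565/0.95 = 3.0 on placebo. The difference therefore widens. It narrows in the first three rows because placebo is assumed to lose more failures.

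**The case against.** The best reply is that little depends on this. ITT is the primary population for all efficacy analyses, the mITT repeat keeps every dosed participant, and nothing legible in the protocol ties a decision to the PP result. This stands, and it sets the severity.

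The affected group may also be small. Investigator-evaluated diarrhea goes to the AB (Section 7.1.2.1), so many true recurrences followed by exit will carry an adjudicated result and be kept. This stands too: no figure in the protocol supports any of the dropped shares used above.

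Section 8.4.1 describes the endpoint as based on adjudication, which might seem to justify the PP clause. But Section 2.1 assigns recurrence without AB confirmation, and in the Part B case against an AB ruling. The PP clause follows only part of that definition.

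The SAP takes precedence on analysis details (Section 8.2) and may refine the PP set. It is not at hand, and the protocol itself fixes this wording, so the clause is a stated rule and not an omission.

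Finally, leaving withdrawals and losses out means that some Section 2.1 failures remain excluded. That is true. The line proposed here runs between an observed C. difficile-related event and an unknown outcome, and it is a convention.

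A reader might infer more: that the clause biases PP against CP101, or that every non-adjudicated failure disappears. The documents support neither. The direction depends on unstated shares in each arm, and rescue users who reach Week 8 remain.

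**Conclusion.** The mismatch is real and minor. Sections 8.3, 2.1 and 8.4.1 together remove from the PP repeat some participants whom the primary analysis counts as C. difficile-related failures, according to how the failure was established. PP recurrence is lowered in each affected arm. In the cases shown the treatment difference moves by 0.4 to 1.6 points downward, or by 0.7 upward; the sign cannot be predicted from the protocol. These sizes rest wholly on assumed adjudicated rates and dropped shares. The Part B component also rests on reading the 8 weeks as Part A follow-up. The ITT and mITT analyses are untouched.

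**What to change.** In the PP definition of Section 8.3, keep completion of 8 weeks and replace the alternative that requires an adjudicated recurrence with: *met the Section 2.1 recurrence definition through a C. difficile-related event before Week 8 (adjudicated recurrence, rescue medication for CDI, C. difficile-related diarrhea with discontinuation, or entry into Part B)*. Naming Part B entry also settles how those participants count.

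State whether deaths and debilitating events are retained, and run a sensitivity analysis the other way. Withdrawals of consent and losses to follow-up may stay excluded as missing outcomes.

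The cost is one clause in the protocol, matched in the SAP, and one additional supportive run. Endpoint, alpha and sample size do not change. The downside is that PP will contain some failures that the AB did not confirm, as the primary analysis already does.

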# 8.4 Efficacy Analysis

#### 8.4.1 Primary Endpoint

The primary efficacy endpoint is defined as the proportion of participants with CDI recurrence through Week 8 based on adjudication calculated as the number of participants with CDI recurrence through Week 8 divided by the total number of participants in the analysis population. Investigator evaluation of a new episode of diarrhea will be adjudicated by an independent AB to confirm CDI recurrence in a blinded fashion prior to database lock.

For the primary efficacy analysis, the active treatment group will be compared to the placebo group.

The primary efficacy endpoint analyses will be repeated using the mITT and PP populations defined in Section 8.3.

# 8.4.2 Secondary Endpoints

#### 8.5 Safety Analysis

All safety summaries and analyses will be performed on the Safety population. All participants will be summarized according to the treatment received.

Safety will be evaluated by presenting summaries of AEs, vital signs, and laboratory evaluations. For each safety parameter, unless otherwise stated, the last assessment made prior to the administration of IP will be used as the baseline value for all analyses.

# 8.5.1 Clinical Laboratory Evaluations

Descriptive statistics for clinical laboratory tests for hematology, chemistry, and coagulation listed in Table 2 will be presented by trial visit as well as the change from baseline.

Laboratory abnormalities will be graded according to NCI-CTCAE Version 5.0, (for analytes where Common Terminology Criteria for Adverse Events (CTCAE) grading applies). The number and percentage of participants experiencing treatment-emergent graded toxicities will be summarized by treatment group and severity grade. A shift table, presenting the 2-way frequency tabulation for baseline and the worst post-treatment value according to the NCI-CTCAE grade, will be provided by treatment group. For laboratory parameters with no CTCAE grading, shift tables (with categories of low, normal, high) from baseline to worst post-treatment value will be provided by treatment group. Both scheduled and unscheduled post-treatment values during the treatment period will be considered.

All clinical laboratory data will be listed. Values outside the normal ranges will be identified in the data listings with flags for low and high.

# 8.5.2 Adverse Events

Any AE reported on the CRF that occurs during or post the administration of IP is defined as TEAE. Additionally, it will be assumed that an AE that was reported to have started at Randomization (Day 1) without an associated onset time may have occurred after the administration of IP. Hence, AEs occurring at Randomization (Day 1) with no associated onset time are assumed to be treatment-emergent.

For the primary safety endpoint, the incidence rate of TEAEs will be presented by treatment group through Week 8.

For the other safety endpoints, the incidence rate of TEAEs and TESAEs will be presented by treatment group through Week 24.

In addition, an overview of TEAEs will be provided which summarizes the incidence of the following information:

- All TEAEs
- Drug-related TEAEs
- Maximum severity of TEAEs
- Deaths
- SAEs

The number and percentage of participants who experienced at least 1 TEAE will be presented by MedDRA system organ class and preferred term. Drug-related TEAEs, withdrawals due to TEAEs, and all SAEs will be summarized in the same manner.

# 8.5.3 Summaries of Baseline Characteristics, Demographics, and Other Analyses

Descriptive statistical methods will be used to summarize all trial data. Unless stated otherwise, the term "descriptive statistics" refers to number of participants (n), mean, median, standard deviation, minimum, and maximum for continuous data, and refers to frequencies and percentages for categorical data. For some data that may be presented as continuous variables, there may be scientific reasons to present those data in constructed

categories as well (e.g., BMI). Reasons for the categories will be described in the clinical trial report. Graphical displays may be presented for selected results.

# 8.6 Biomarker Analysis

# 8.7 Subgroup Analyses and Effect of Baseline Factors

[figure not shown]
Subgroup analysis will include, but is not limited to, the following subgroups based on baseline characteristics and will be used for subgroup analyses for the primary efficacy endpoint in the ITT, mITT, and PP populations. The full details of subgroup analysis will be included in the SAP.

- Age group (< 65 years vs.  $\geq$  65 years)
- Age group (< 70, 70-79, and  $\geq$  80 years)
- Gender group (male vs. female)
- Race group (White vs. others)
- Charlson Comorbidity Index ( $< 3 \text{ vs.} \ge 3$ )
- Previous CDI episodes total number of CDI episode in previous 12 months
- Recurrent CDI category
- •
- Geographical region/country

